2. BACKGROUND & SIGNIFICANCE

Heart failure (HF) is a major health, social and economic problem worldwide ¹. Incidence and prevalence are increasing ², in part due to an aging population and rising burden of comorbidities ³. More than half of the patients with HF present with preserved ejection fraction of the left ventricle (HFpEF) ⁴. The main symptoms of these patients are fatigue and exercise intolerance ⁵. Advances in medical and device therapies have improved mortality in patients with HFrEF ⁶⁻⁹. On the other hand, only recently Sodium-Glucose-Cotransporter 2- inhibitors (SGLT2-i) proved in large randomized clinical trials (RCT) in patients with HFpEF and HFmrEF to reduce the combined endpoint consisting of hospitalization rate and cardiovascular mortality compared to placebo. This effect was mainly driven by reduced hospitalization ^{10,11}. Thus, there is still unmet need to improve symptoms, quality of life, morbidity, and mortality in these groups of patients. As a result, further drugs or interventions are still required.

Although patients with HFpEF have preserved EF there is still severe exercise intolerance, primarily due to reductions in peak cardiac output (CO) and peripheral arterial-venous oxygen difference (A-VO₂ Diff) ^{12,13}, as well as a proposed impairment of skeletal muscle oxidative metabolism ¹⁴. There is a continuously increasing volume of evidence showing that peripheral factors such as skeletal muscle function plays a crucial role in explaining the reduced exercise capacity in patients with HF with reduced ejection fraction (HFrEF) and with HFpEF ^{15,16}. Some studies showed that exercise intolerance can remain for several months after heart transplantation and achieving improvement of cardiac output ¹⁷. Furthermore, exercise training improves exercise tolerance in patients with HF independent of improving cardiac function ¹³. Both examples show that skeletal muscle function may play a central role in explaining the limited exercise capacity in patients with HF ¹⁸.

The changes of skeletal muscle occur on various levels. This could include loss of skeletal muscle mass, replacement of muscle with fat tissue and reduced muscle strength ¹⁹. Several alterations on the molecular level accompany the above-mentioned changes and include reduced protein synthesis through blunting of the anabolic insulin-like growth factor 1 (IGF1) signaling pathway ²⁰, and/or increased protein degradation including activation of the ubiquitin-proteasome system (UPS) ²¹, autophagy ²² and apoptosis ²³. Further metabolic and mitochondrial dysfunction are well described in the cardiac myocytes ²⁴ and to a less extent in skeletal muscle.

Through transcriptional profiling, a set of ~120 response genes, or atrogenes, has previously been identified in atrophying muscles 25 . Dysregulation of atrogenes occurs in muscle atrophy, including genes required for ATP production and transcripts for extracellular matrix proteins. Further, protein quality control mechanisms in the cell are closely controlled by cellular autophagy and dysregulation of autophagy has been linked to abnormal protein turnover and overall cellular dysfunction. Dysregulation of autophagy has been linked to abnormal protein turnover in the failing myocardium and skeletal muscle. Suppression of PGC-1 α , a central regulator of metabolism and mitochondrial biogenesis, was found in the setting of muscle atrophy 26 . Induction of PGC-1 α in rodents prevents muscle atrophy and transcription of atrogenes 27 . However, less is known in this regard in HFpEF patients.

Reduced muscle mass and function in patients with HF could be triggered additionally by the activation of the sympathetic nervous system, renin-angiotensin-aldosterone system ²⁸, proinflammatory cytokines ²⁹, and transforming growth factor β family such as myostatin ³⁰. The resulting imbalance between anabolic and catabolic pathways, in favor of catabolic cascade in patients with HF, is very important in explaining the muscle atrophy, reduced muscle mass and function in these patients. Structurally, changes such as reduced size and number of muscle fibers, a switch from slow muscle fibers MHC I to the fast one's MHC II and reduced capillary density have been described in patients with HF³¹.

These changes have been studied mainly either in animal experiments or on patients with HFrEF. But not much is known about patients with HFpEF.

The only proven therapy so far to improve exercise capacity, dyspnea, and QoL in patients with HFpEF is exercise training ³². However, there are two concerns related to exercise training. The first one is the compliance of patients. Secondly, patients with HF have often reduced mobility due to sarcopenia, cachexia or frailty ^{16,33}. Therefore, new interventions and innovations need to be investigated.

Intermittent hyperthermia such as sauna represents a good alternative to the above-mentioned limitations. Moderate Sauna could be equal to low-and moderate-intensity physical exercise training. Heart rate may increase up to 100/min ^{34,35}. In one large (2315 proband) prospective population-based cohort-study in middle-aged men from Eastern Finland with a follow-up of 20.7 years, increased frequency and length of sauna sessions were associated with reduced sudden cardiac death, coronary heart disease (CHD), and fatal cardiovascular disease 36. Some other studies proved improved endothelial function in patients with CHD and HF and shown that sauna is safe in patients with HF and led to improvement of left ventricular ejection fraction and exercise capacity as well as to reduction of natriuretic peptides and arrhythmias ³⁷⁻³⁹. A small study on 6 male distance runners who had one sauna session of 30 minutes twice a week for 3 weeks showed 32% improvement in endurance compared to baseline 40. Furthermore, two 60-minute sessions of whole-body hyperthermia (44°-50° C) and 50% humidity with one week pause showed increased activity of the anabolic cascade in skeletal muscle represented by Akt/mTOR pathway, which is a crucial regulator of skeletal muscle mass 41. Another small interventional study found that daily locally applied heat treatment to skeletal muscle during immobilization period of 10 days in humans prevented the loss of mitochondrial function, increased heat shock protein (HSP), and reduced skeletal muscle atrophy by 37% compared to a sham treatment group 42.

A further suggested important effect of sauna is enhancing the cognitive and mental health. Whole-body hyperthermia for example via hot water baths in healthy males stimulated a strong increase in serum brain-derived neurotrophic factor (BDNF) levels ⁴³. BDNF is a protein that activate the growth of new neurons both in the peripheral and central nervous system. BDNF modulates and improves anxiety and depression ⁴⁴. A small RCT in 28 patients with mild depression showed, compared to the control group which received bedrest, that patients who were exposed to sauna had reduced symptoms of depression and anxiety and reported improved appetite and reduced somatic complaints ⁴⁵ (figure 1).

All the potential benefits of sauna seem to be comparable to exercise training with even some more advantages as discussed above. A comprehensive systematic conducted study in patients with HFmrEF and HFpEF to investigate the feasibility of intermittent hyperthermia (sauna) as intervention and the effect of sauna on cardiac function, exercise capacity, skeletal muscle function from bench to bedside, as well as on cognitive capacity, is still missing.

[figure not shown]

Figure 1: Heat shock proteins (HSPs), which are provoked during sauna, provide protection against cellular stress.

HSPs prevent protein disorder and aggregation by repairing proteins that have been damaged, providing protection against chronic diseases. Increased expression of HSPs also slows muscle atrophy and promotes longevity. (Modified from Patrick, R. P.; Johnson, T. L. Sauna use as a lifestyle practice to extend healthspan. Exp Gerontol 2021, 154, 111509).

3. PRELIMINARY STUDIES

The applicant is a heart failure specialist, who has experience in performing and interpreting cardiopulmonary exercise testing (CPET) and in evaluating the structure, function, and metabolism of skeletal muscle in HF patients.

The applicant has previously studied the role of muscle function and the prevalence of muscle wasting (sarcopenia) in Heart Failure patients with preserved Ejection fraction (HFpEF) at the Charité, Humboldt University, Berlin.

In one study, a total of 117 symptomatic outpatients with HFpEF were enrolled prospectively in Germany, England, and Slovenia as part of in a multi-center European study (SICA-HF). Appendicular skeletal muscle (ASM) mass (the sum of muscle mass in both arms and legs) was assessed by dual energy X-ray absorptiometry. Echocardiography, 6-minute walk testing (6-MWT), muscle strength assessment, CPET and quality of life (QoL) evaluation were performed. Muscle wasting was defined as ASM 2 standard deviations below the mean of a healthy reference group aged 18-40 years. Patients were divided into 3 groups according to the E/e' value as group $A \le 8$, group B 9-14, and group $C \ge 15$. **Muscle wasting was present in 19.7% of all patients**. These patients performed worse in 6-MWT and showed lower absolute peak oxygen consumption. Values of muscle strength/ASM were associated with a better QoL. Logistic regression showed ASM to be independently associated with reduced walked distance in 6-MWT adjusted for NYHA, height, left atrium diameter, ferritin and forced expiratory volume in 1 second (FEV1) 16 .

Furthermore, in a further project financed through a grant from the interdisciplinary center for clinical research in the University Hospital Jena, [name] performed a comparison among HFpEF, HFrEF and HC regarding skeletal muscle function, structure and metabolism. We found that HFpEF patients have reduced muscle function, reduced mitochondrial size and elevated levels of atrophy-related genes and protein (FBXO-32, MSTN-2) compared to HFrEF and HC. Perturbations in fatty acid oxidation and glucose metabolism as well as reduced mitochondrial volume density were noted in HFpEF and HFrEF patients compared to HC. These changes were associated with reduced exercise capacity. The results remained unchanged after adjusting for age and gender.

By dividing the cohort into two groups according to the mean value of muscle endurance, we described for the first time the molecular, metabolic and clinical profile of reduced muscle endurance and found that patients with reduced muscle endurance showed reduced gene expression of slow muscle fibers myosin (MYH 7), and elevated levels of atrophy genes and proteins (TGF- β1, FOXO-1, UBB, TRIM63, FBXO-32), and lysosomal gene (CTSL). Furthermore, the expression of PPARα and GLUT4 were reduced in these patients. This was associated with an elevated inflammatory biomarker level (GDF-15) and reduced values of peak VO₂ and 6MWT. There was neither an association with age nor with physical daily activity estimated in the QoL-questionnaire ⁴⁶.

The metabolic profile of patients with reduced muscle endurance (RME) among HFpEF and HFrEF patients showed two different metabolic profiles and likely different activation of metabolic pathways. Furthermore, we presented a clear association between metabolic and functional changes occurring in skeletal muscle and the metabolomic profiles found in serum in patients with HF. Additionally, we showed for the first time in HFpEF patients with RME elevated levels of Kyn. Kyn correlated with elevated inflammatory biomarker levels, was an independent predictive factor for RME, and showed very high sensitivity and specificity (AUC 0.83) in detecting RME. One of the most novel findings of this study was showing several indices of mitochondrial dysfunction and perturbations fatty acid oxidation in multiple levels in patients with HFpEF and RME such as a reduction of long-chain and medium-chain ACs, and a decrease of the ratio of medium-/long-chain-ACs. Studies in obese patients with diabetes, and in those on high fat feeding have shown, increased rather than decreased rates of β -oxidation in skeletal muscle ⁴⁷. The high rates of fatty acid catabolism in insulin-resistant muscles were attributed principally to "incomplete" fat oxidation, where a large proportion of fatty acids enter the mitochondria but are only partially degraded. ⁴⁸.

These novel findings indicate the development of an intrinsic skeletal myopathy impairing muscle performance contributing to increased fatigue and frailty in HF.

In a further related publication [name] et al. found that outpatients with HFpEF had worse QoL and higher anxiety and depression scores compared with HFrEF and non-HF controls. Depression was associated with reduced QoL and was an independent predictor for reduced coordination capacity in these patients ⁴⁹.

Furthermore, we showed recently that novel cardiac markers such as left atrial strain (LAS) might be capable to demonstrate the link between cardiac and peripheral limitations of exercise capacity ⁵⁰. We found in this study in patients with HFpEF and HFrEF that reduced LAS was a sensitive detector for reduced skeletal muscle endurance in these patients with area under the curve AUC (0.8).

Altogether, these data demonstrate that the applicant has ample experience testing exercise function in HF, specifically with cardiopulmonary exercise and skeletal muscle functional testing. Furthermore, the applicant has experience working with muscle tissue and bench science techniques and will be supported by an established group of clinical-translational investigators in the lab of [name].

The next logical step would be to investigate if an intervention such as sauna is safe and if it could reverse these symptoms and manifestations. If this will be proved to be correct, we will plan a larger scale trial.

Our results will likely give a new direction for future research especially in patients with HFpEF This might finally have direct therapeutic implications. We plan as a next step a RCT to confirm our results.

4. AIMS and Hypothesis

The aim of the study is to test the safety and efficacy of intermittent hyperthermia (sauna) in a pilot study on patients with HF. We will compare the results among patients with HFmrEF, and HFpEF regarding cardiac function, exercise capacity, skeletal muscle structure and function, metabolomic changes, cognitive function and quality of life both at baseline and after the intervention with sauna.

Hypothesis: We hypothesize that intermittent hyperthermia (sauna) is a feasible intervention in patients with HF regardless of LVEF. Exploratively we will test the effect of the intervention on filling pressure (E/é) as well as on the level of NT-pro-BNP. Peripherally, skeletal muscle function (including metabolic and mitochondrial function) and structure. Finally, the effects of the intervention on QoL and of cognitive function will be tested.

Questions to be answered through our investigation, and how:

- 1) Is hyperthermia intervention (sauna) feasible in patients with HF?
- 2) Does sauna improve exercise capacity? (CPET, 6MWT, skeletal muscle strength and endurance).
- 3) Does sauna improve cardiac function (Echocardiography).
- 4) Understanding the related pathophysiology of the observed results on skeletal muscle and exercise capacity on molecular and mitochondrial level (skeletal muscle biopsies and the following tissue analysis parallel to blood analysis).
- 5) The role of inflammation in the altered muscle structure and function and its possible reversibility through sauna. (Skeletal muscle biopsies: NFkB and NEMO).
- 6) Observing changes in QoL and mental health (depression and anxiety). This will be evaluated by questionnaires as well as by testing the hypothesis that correlates Kynurenine to depression and inversely to exercise (here sauna). (Kyn levels both in skeletal muscle biopsy samples and in serum both at baseline and at the end of the intervention).

While the main aim of the current study is to answer the first question, we might get some level of evidence to answer the other questions. This would support planning the next and larger study.

5. RESEARCH DESIGN & METHODOLOGY

Study Population: HF patients will be recruited from in the clinic of cardiology and angiology in the University Hospital in Magdeburg. The HF outpatient clinic includes a diverse group of both men and women; therefore, study subjects will not be limited by gender. Altogether, 30 patients, 15 in each group will be recruited prospectively and will enter the final analysis. At least 12 patients per group will be analysed with an expected drop-out-rate of 20%. Stratifications will be performed regarding sex and age to guarantee similar distribution in and among these groups.

1.1.1. Inclusion Criteria

- NYHA class II or III, clinically stable in the previous three months
- Females and males, age \geq 50 years
- Left ventricular EF ≥50%, and at least 2 of the following: left atrial volume index (LAVI ≥34ml/m²) or E/e² >9 or interventricular septal thickness >12mm or pulmonary arterial pressure >35mmHg (non-invasive measurement) for HFpEF. HFmrEF will be defined as recommended according to the ESC-HF-guidelines similarly to HFpEF, however with 50 > LVEF ≥ 40.
- Stable on standard HF medication according to the ESC-HF guidelines in the last 4 weeks.

1.1.2. Exclusion Criteria

- Major cardiovascular event or procedure such as myocardial infarction, percutaneous coronary intervention (PCI), aortocoronary bypass operation in the previous 3 months.
- Patients who have an indication for dual platelet inhibition.
- Stroke.
- Patients who have mechanical heart valves.
- Pulomary embolism.
- Deep vein thrombosis.
- Patients with implanted cardiac devices.
- Severe valvular disease
- Individuals with altered or reduced sweat function, such as in autoimmune diseases, spinal cord injuries, Fabry disease.
- Symptomatic hypotension regardless of the measured value and those with BP systolic <110mmHG
- Patients on oral anticoagulation for other reasons than atrial fibrillation
- Uncontrolled diabetes mellitus (HbA1c>8%), severe renal dysfunction (GFR<30ml/min), or pulmonary disease (COPD GOLD ≥3)
- Primary muscle disorder (e.g. muscular dystrophies)
- Neurological disease (e.g. Dementia, Parkinson)
- right ventricular dysfunction
- uncontrolled arrythmias
- Any condition that in the opinion of the investigator could prohibit performance of 6-MWT.

STUDY PROTOCOL: All participants will undergo a standardized series of assessments as shown in table 1. In case of clinical improvement, these benefits are likely to diminish over time if sauna bathing is discontinued. To address this, patients will be invited for a follow-up visit three months after completing the intervention. All investigations will be repeated, except for the skeletal muscle biopsy.

Table 1: Timetable of the study

	Week 0	Week 1	Week	Week 13	Week 14	Week 30
	Visit 1	Visit 2	2-12	Visit 3	Visit 4	Visit 5
Informed consent	X					
Echocardiography	X			X		X
Cardiopulmonary exercise test (CPET)	X			X		X
6-MWT		X			X	X
Blood tests		X			X	Х
QoL-questionnaire	X			X		X
Accelerometer	X			X		х
isokinetic skeletal muscle measurement	X			X		
Skeletal muscle biopsy		Х			X	
Sauna Intervention (twice weekly)			Х			

METHODOLOGY

Echocardiography: The diameter, size, and function of all 4 chambers will be measured through transthoracic echocardiography. Valve functions as well as the diastolic function will be evaluated. Strain analysis of the left and right ventricle and of the left atrial will be performed as well.

Cardiopulmonary Exercise Testing: Bicycle exercise testing in association with air-gas-exchange is considered to be a good non-invasive method for estimating functional capacity and will be performed in all individuals by [name] ⁵¹. We routinely perform CPET in patients with HF. The applicant has used the technique in multiple research investigations and in clinical daily work. Subjects will perform a ramp biking exercise on an electronically braked cycle ergometer as previously described ⁵².

Bioelectrical-Impedance Analysis (BIA): It is a non-invasive measurement of the body composition, i.e. muscle, fat, water. Measurements will be performed when patients are in supine positions with arms

lying along the body sides. 4 electrodes will be connected to hands and arms. Patients who have implanted cardiac devices will be excluded ⁵³.

Muscle Strength and Fatigability: For the specific assessment of skeletal muscle function and fatigue, measures of isolated muscle group strength, endurance, and fatigability will be analyzed in association with overall functional capacity. Isokinetic measurements will be completed on the extremities, using the Biodex System 4 Pro (Biodex Medical Systems, Shirley, NY), as shown in **Figure 2**. Isokinetic data will be collected to measure PKTQ/SM, work to body weight (WK/BW), average power, endurance, fatigability, time to peak torque, acceleration and deceleration time. Muscle strength will be further analyzed through the use of hand grip strength ⁵⁴, repeated three times on both dominant and non-dominant hands.

Six Minute Walk Test: The six-minute walk test is a commonly used clinical tool, which allows testing of the functional capacity in HF patients in a "real-life" setting. Using standard methodology ⁵⁵, patients will be asked to walk as fast as possible on a 25-meter course for 6 minutes. The test will be scored in rounded meters walked in 6 minutes.

Questionnaire tools to complement functional assessment measurements: To assess measures of daily activity of patients with HF, we will utilize two questionnaires that assess physical limitation, symptoms and quality of life (QOL). The Kansas City Cardiomyopathy Questionnaire ⁵⁶ as well as HADS-questionnaire ⁵⁷will be used to measure disease-specific health related QOL.

Serum analyses: Serum will be obtained from all individuals at the time of CPET and muscle biopsy, to assess changes in serum biomarkers. Standard phlebotomy technique in sterile fashion will be utilized. Serum samples will be analyzed for several biomarkers (IGF-1, myostatin, insulin, growth hormone) which will complement the skeletal muscle assessments. We will use western blot techniques ⁵⁸ and commercially available ELISA kits (R&D, USA).

Metabolomic analysis and Lipidomics:

Altogether 188 metabolites (ACs, AAs, biogenic amines, glycerophospholipids, sphingolipids, and sugars) will be quantified in serum using the AbsoluteIDQTM kit p180 (Biocrates Life Science AG, Innsbruck, Austria). The measurement will be performed after exercise (CPET) both in skeletal muscle and serum, and at rest in serum (Figure 3). Circulating fatty acids and ceramide levels will be analyzed in both the serum and skeletal muscle using LC/MS lipidomics. Total lipids will be isolated using the Forch method. Analysis will be performed in collaboration with the Institute of Clinical Chemistry ⁴⁷.

[figure not shown]

Figure 3: Metabolomic profiles of patients with reduced muscle endurance (RME) vs. preserved muscle endurance (PME) in HFpEF vs. HFrEF suggest different distorted metabolites and likely different mechanisms and metabolic pathways accompanying the RME. Visualization of the metabolomic profile using heat maps to show changes in the top 25 metabolite concentrations, and partial least squares-discriminant analysis (PLS-DA) among HFpEF ((A), A-1 and A-2), HFrEF ((B), B-1 and B-2), and in patients with RME and HFpEF vs. RME and HFrEF ((C), C-1 and C-2), respectively ([name] et al. Cells 2022).

Skeletal muscle biopsies: Obtaining muscle tissue from all individuals will allow us to study the effect of sauna on skeletal muscle both structurally and functionally. Skeletal muscle biopsies will be performed by [name], who has performed several series of biopsies (>50 biopsies) without complications. Aspirin, oral anticoagulation as a therapy for atrial fibrillation will be held for two days (the day prior to the muscle biopsy and the day of the muscle biopsy). Other indications for oral anticoagulation are contraindications in our study. Patients will lie comfortably in the supine position for biopsy of the vastus lateralis muscle in the right leg. Biopsy sites will be prepped with betadine and 2% xylocaine (without epinephrine), with a small stab cut then completed with a blade scalpel. A 5 mm Bergstrom muscle biopsy needle will be used to remove 100-200 mg muscle tissue. After harvesting the first sample, the needle will be rotated 90 degrees and a second sample will be extracted to maximize yield for analysis. The wound site will be closed with steri-strips and a sterile pressure bandage. One fragment of the biopsied muscle will be frozen in liquid nitrogen cooled isopentane for histomorphological and enzymatic analysis. The second fragment will be cut and placed in cryotubes containing RNA preservation solution (RNAlater) and immediately frozen in liquid nitrogen. All samples will be stored at -80°C. Analyses will be performed blinded. The patients will be asked to return for reassessment of the wound site ⁵⁹.

A systematic review shows a very low incidence of complications (total 0.15%, 22 complications in the course of 13914 muscle biopsies in children and adults from different muscles [M. quadriceps femoris, M. deltoideus, M. biceps humeri) (Tarnopolsky et al. 2011). These were local skin infections (8 cases), arterial bleeding (2 cases), pain symptoms (>3 days, 5 cases), cutaneous nerve injuries (5 cases), and hematomas (2 cases) ^{60,61}.

All of the following analyses will be performed before and after the intervention.

Oxidative Capacity: Fatty acid oxidation will be analyzed in muscle tissue of all subjects by measuring the production of $[^{14}C]$ CO₂ from $[_{14}C]$ oleic acid.

Electron microscopy: We will analyze mitochondria and lipid droplet accumulation in the skeletal muscle using electron microscopy. In brief, after glutaraldehyde fixation and resin embedding, the tissue is micro-sectioned and imaged by scanning electron microscopy under computer-guidance for analysis and image preparation (Figure 3).

[figure not shown]

Figure 3: Transmission electron microscopic images of mitochondria in skeletal muscle biopsies in patients with HFpEF, HFrEF and controls ([name] et al. Circulation HF 2020).

mRNA Expression: We will analyze mRNA expression of genes related to muscle atrophy in the muscle biopsy specimens from HF patients and controls. Further, we will analyze gene sequences that code for metabolic marker genes related to muscle atrophy in the muscle biopsy specimens from HF patients and controls. As discussed above, these genes belong to a specific set of atrophy genes, so called atrogenes, which were previously characterized to be upregulated in several models of skeletal muscle atrophy ²⁵. We specifically choose to analyze the expression of these genes since they have been associated with muscle atrophy in several animal models and together seem to form a genetic fingerprint of muscle atrophy. We will particularly focus on atrogin-1 and MuRF-1, but all the following gene sets will also be analyzed:

- Protein degeneration atrogenes: atrogin-1/MAFbx, MuRF1, Polyubiquitin, E3α-II, proteasome subunits, cathepsin L.
- Growth factors: IGF-1, IGFBP5, FoxO1, TGFα, myostatin, follistatin.
- Markers of cellular metabolism. mCPT1, the rate-limiting mitochondrial fatty acid-transferring enzyme; CPT2, MCAD, a representative fatty acid β-oxidation enzyme; PPARα, a key transcriptional regulator of fatty acid genes; PGC-1α, UCP3; GLUT1 and 4; and PDK-4.

Proteomics: To further assess molecular changes of the muscle proteome, we will also analyze changes in protein levels of the above-mentioned genes. Total muscle proteins will be obtained using extraction buffer containing sodium fluorate, protease and phosphatase inhibitors without detergent and centrifugation. Samples will be stored at -80°C until the analysis. Protein lysates will be used for the analysis of changes in proteasome content and activity. Also, changes in the expression of specific genes (e.g. myosin heavy chain) will be investigated on the protein level using western blot techniques as previously described ⁵⁸ (**Figure 4**). **Further, we will perform a post-translational modification analyses and global proteome analysis of the entire skeletal muscle proteome.**

[figure not shown]

Figure 4: CPT1B-protein level in patients with HFpEF, HFrEF and in HC measured by western blot. *: p<0.05.

Autophagy: To assess catabolic mechanisms in the skeletal muscle tissue, we will measure LC3I and LC3II using standard western blot techniques and LC3II staining on tissue immunohistology specimens.

Intermittent hyperthermia sessions (sauna):

All participants will be accompanied by medical doctors for two sessions weekly, each between 8-15 minutes. The intervention will be done in the NEMO-sauna in Magdeburg. The duration of the intervention will be 10 weeks. We will start the first 2 weeks with 8 minutes. Week 3-4: 10 minutes, week 5-6: 12 minutes, week 7-10: 12-15 minutes. Sessions will be done in groups each consisting of 5 patients. The temperature of the sauna will be 60°C. After each session a cold shower will follow and then rest for 20 minutes. Blood pressure, heart frequency, O2-Saturation will be measured prior to each session as well as directly after the shower and at the end of the rest.

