9. STATISTICS

There is not enough prior data to calculate the sample size. Our aim is to test primarily the safety of intermittent hyperthermia and the feasibility of the intervention on patients with HF. We still do think based on our previous research and in spite of the small sample volume, that we would find some significant differences in the secondary endpoints comparing baseline data to post intervention.

All data and statistics will be reported as mean \pm standard deviation (n \pm SD) for continuous normally distributed data or as median and interquartile range [25–75%] for variables that were not normally distributed, respectively. Categorical data will be summarized by percentages. The Statistical Package for Social Sciences software (SPSS 26, IBM, Armonk, USA) will be used for statistical analysis. The chi-squared test will be used to look for trend for categorical variables and Kruskal Wallis test will be applied for not normally distributed data, respectively. Analysis of variance (ANOVA), Pearson's or Spearman simple regression will be used as appropriate. A two-tailed p-value <0.05 indicates statistical significance.

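### Blinding is specified only for the muscle biopsy analyses; no masking to visit is specified for reading echo or CPET recordings, although every participant is treated

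*Protocol*

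**What the plan says.** The one blinding statement in the protocol is "Analyses will be performed blinded". It comes in the Methodology paragraph on skeletal muscle biopsies, directly after sample storage, so on a plain reading it covers the tissue work. It does not say whether the analysts are blinded to visit, disease group or patient.

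The Echocardiography paragraph covers chamber size and function, valve function and diastolic function, and adds: "Strain analysis of the left and right ventricle and of the left atrial will be performed as well". The Cardiopulmonary Exercise Testing paragraph describes the test as a "non-invasive method for estimating functional capacity and will be performed in all individuals by" one operator, whose name is removed in the public text. Neither paragraph says who reads the recordings, when, or under what masking.

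Table 1 schedules echo and CPET at Visits 1, 3 and 5 (weeks 0, 13 and 30). The sauna paragraph describes a single regimen for everyone: "All participants will be accompanied by medical doctors for two sessions weekly, each between 8-15 minutes". The two groups, HFmrEF and HFpEF, are disease strata and not treatment arms.

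On the rank of these endpoints, section 4 says: "Exploratively we will test the effect of the intervention on filling pressure". Section 9 makes safety and feasibility primary, and then expects that "we would find some significant differences in the secondary endpoints comparing baseline data to post intervention", judged at a two-tailed p-value below 0.05.

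**The concern.** Strain and diastolic indices depend on choices by the reader, such as which beats to use and where to trace borders. Some CPET variables can depend on reading in the same way. In a study where everyone is treated between Visit 1 and Visit 3, knowing the visit is the same as knowing the exposure. A reader who expects improvement can shift later readings slightly, and the shift goes straight into the baseline-to-post contrast that section 9 intends to test. No untreated arm is described that would carry the same shift and let it be subtracted.

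What is at stake is how to interpret the answers to questions 2 and 3 in section 4 (exercise capacity and cardiac function), which the protocol says would support planning a larger study. The sponsor guards against this bias in the laboratory. The protocol does not extend that safeguard to the clinical recordings.

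**Working it through.** **Plan's own figures.** Section 5 gives 15 recruited per group, 20% dropout and at least 12 analysed per group. These agree: 12 / (1 − 0.20) = 15, and 15 × 0.80 = 12. In total, 30 are recruited and at least 24 analysed. Section 9 states that no sample size was calculated, so there is no effect size, SD or power to reproduce.

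**Inputs for the illustration.**
- From the protocol: two-sided alpha 0.05; 24 pairs (both groups) or 12 pairs (one group).
- Assumed, because the documents give no value: a true change of zero; a mean reading shift b of 0.1 to 0.3, in SDs of a single measurement; a correlation r between repeat measurements of 0.5, 0.8 or 0.9.
- Also assumed: a paired t-test. Section 9 names no paired test for the before-after comparison.

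**Formulas.**
- SD of the change, in units of the single-measurement SD: √(2(1 − r)).
- Standardised shift: d = b / √(2(1 − r)).
- Noncentrality: d√n. The rejection rate is the two-tailed probability of a noncentral t with n − 1 degrees of freedom beyond the 5% critical value (2.069 for n = 24, 2.201 for n = 12).

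**One case in full.** With r = 0.8, the SD of the change is √0.4 = 0.632. With b = 0.2, d = 0.2 / 0.632 = 0.316. With n = 24, the noncentrality is 0.316 × √24 = 1.549, and the rejection rate is 31.8%.

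**Rate of p < 0.05 with no true effect, one endpoint.**

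| Pairs | Correlation | SD of change | Shift 0.1 SD | Shift 0.2 SD | Shift 0.3 SD |
|---|---|---|---|---|---|
| 24 | 0.5 | 1.000 | 7.6% | 15.6% | 29.1% |
| 24 | 0.8 | 0.632 | 11.5% | 31.8% | 60.5% |
| 24 | 0.9 | 0.447 | 18.3% | 55.5% | 88.2% |
| 12 | 0.8 | 0.632 | 7.9% | 17.1% | 32.3% |

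With no shift, every row is 5%. A shift of 0.05 SD at correlation 0.8 with 24 pairs gives 6.6%. The more repeatable the measure, the more a given shift matters, because the noise in the change score is smaller.

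**Which contrast is exposed.** Write the observed change in each group as true change plus shift. The shift stays in each within-patient change. If it is common to HFmrEF and HFpEF, it cancels in the difference between the two changes. The exposure is therefore to the before-after contrast only.

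**The case against.** A reader might infer that echo and CPET are read with the visit known. The protocol does not say so. It is silent, and a reading manual that is not shown may deal with the matter. Blinding the tissue work does not imply that the other readings are unblinded, and the protocol does not contradict itself. This stands, so the point is limited to masking not being specified. It remains a point because unmasked reading would comply fully with the text, and because masking depends on recordings being stored from Visit 1. An analysis plan cannot restore that later.

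A second objection is that these endpoints are not the study's main question: feasibility and safety come first, E/e' is exploratory, and a larger trial is to confirm the results. This also stands and limits the weight of the point. It does not remove it, since section 9 still applies a significance threshold to these endpoints.

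A third objection concerns CPET. The protocol names no threshold or other reader-dependent CPET variable as an endpoint. Much of the expectation effect there would come through encouragement and patient effort, which masked reading leaves untouched; the six-minute walk, handgrip and isokinetic tests share that problem. A single operator also limits between-operator variation and is not in itself a defect. All of this stands. The CPET part applies only to variables that a reader derives from the recording.

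Finally, the size rests entirely on assumed values. That is correct: the table shows what a shift would do, not that one is likely.

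**Conclusion.** The point holds in this limited form. The protocol specifies blinding for the biopsy analyses and specifies no masking to visit for echo reading or for off-line reading of CPET recordings. Because every participant receives sauna, a reading shift would pass undiluted into the before-after change in these secondary and exploratory endpoints.

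Under assumed shifts of 0.1 to 0.3 SD, the nominal 5% error rate for one endpoint would become about 8% to 88% with 24 pairs across correlations of 0.5 to 0.9. It would be 8% to 32% with 12 pairs at correlation 0.8. The width of that range shows how little the documents allow one to say about the actual size.

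Two stronger readings are not supported. The primary safety and feasibility conclusion is not shown to be affected. Nor is the HFmrEF versus HFpEF comparison of changes, where a common shift cancels. The change is worth making because it extends the sponsor's own rule at low cost.

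**What to change.** Extend the biopsy blinding rule to the echo paragraph and to any reader-dependent CPET variable:

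- Store echo loops and CPET recordings from Visit 1 onward.
- Have the same reader measure them with patient code, date and visit masked and the order shuffled.
- Read in one batch after Visit 5. Alternatively, read after all Visit 3 recordings are in, and later read Visit 5 in the same way, mixed with re-masked earlier recordings so that the batch does not reveal the visit.
- Use on-site readings for eligibility and safety only.
- State in the biopsy paragraph what the tissue analysts are blinded to.

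No patient, visit, procedure, sample size or alpha changes, and no extra reader is needed. Section 14 already provides for pseudonymised study data, so the files need only relabelling and shuffling. The cost is some reading time and later echo results, which sits against the intention in sections 6 and 12 to analyse immediately; the two-stage option reduces that delay. In a sample of 30 the reader may still recognise some patients. Masked reading also leaves acquisition by staff who may know the visit, encouragement during testing, learning and regression to the mean, and the report should say so.
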